Outcomes after Hypotensive Neuraxial Anesthesia in Total Hip Arthroplasty

FUNDER: Department of Anesthesiology

PROTOCOL NO.: 2018-2235

VERSION & DATE: 12/5/2018

TABLE OF CONTENTS

| | |
|---|----------|
| TABLE OF CONTENTS | 2 |
| PROTOCOL SYNOPSIS | 3 |
| 2.0 INTRODUCTION..... | 5 |
| 3.0 OBJECTIVE(S) OF CLINICAL STUDY | 5 |
| 4.0 STUDY HYPOTHESES | 6 |
| 5.0 STUDY DESIGN | 6 |
| 5.1 Endpoints | 6 |
| 5.1.1 Primary Endpoint | 6 |
| 5.1.2 Secondary Endpoints..... | 6 |
| 5.2 Study Sites | 6 |
| 6.0 STUDY POPULATION | 6 |
| 6.1 Number of Subjects..... | 6 |
| 6.2 Inclusion Criteria..... | 7 |
| 6.3 Exclusion Criteria | 7 |
| 7.0 PROCEDURES..... | 7 |
| 7.1 Data Collection | 7 |
| 8.0 STATISTICAL ANALYSIS..... | 8 |
| 9.0 ADVERSE EVENT ASSESSMENT | 8 |

PROTOCOL SYNOPSIS

| | |
|--------------------------------|--|
| Protocol Title: | Outcomes after Hypotensive Neuraxial Anesthesia in Total Hip Arthroplasty |
| Protocol Number: | 2018-2235 |
| Protocol Date: | |
| Sponsor: | Department of Anesthesiology |
| Principal Investigator: | [name], PhD |
| Objective: | The proposed project will be the largest study on deliberate hypotensive neuraxial anesthesia and adverse outcome in THA. It will provide essential feedback and guidance to our clinical practice, indicating whether we need to modify our intraoperative management for better patient outcomes and less adverse complications, or conversely may allow us to argue that deliberate hypotensive neuraxial anesthesia is not associated with adverse events. This will be the first significant database study to examine the clinical outcomes of patients undergoing THA with a deliberative hypotensive neuraxial anesthetic technique. |
| Study Design: | Retrospective study |
| Enrollment: | 10,000 |
| Subject Criteria: | All primary THA patient data with sufficiently complete intraoperative vital signs will be included in the study. |
| Data Collection: | Sources: Medical record Variables: 
• MRN• Age• BMI• ASA status• Ethnicity• Gender/sex• zip code• insurance• type of surgery• primary anesthetic type• anesthetic procedures• anesthesia provider name• anesthesia provider helpers (CRNA, Resident, Fellow)• surgeon• duration of surgery• duration of anesthesia |

| | |
|------------------------------|--|

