2.0 INTRODUCTION

There have been long debates in regards to the appropriate blood pressure management during joint replacement. Traditionally at HSS, many anesthesiologists routinely manage the blood pressure in the 40-60 mmHg MAP range to minimizing perioperative bleeding and optimize surgical outcome. Such deliberate hypotension anesthesia does not seem to cause increased risk of major complications in several studies, including studies from our institution (Paul et al, Can J Anesth 2007; Bombardieri et al, Anesth Analg, 2016; Weinstein et al. RAPM, 2018).

However, concerns still remain due to evidence from other major studies, which indicated increased complication risks with intraoperative hypotension (Salmasi et al, Anesthesiology, 2017; Sessler et al, Anesthesiology, 2018). Previous studies at HSS are mostly limited by the small number of patients, and therefore could not draw more convincing conclusion. With the implementation of EPIC electronic medical record system at HSS in 2016, it is feasible to access thousands of patients' intra-operative data nowadays. Hereby, we propose this project to study whether there is associated between deliberate hypotension and increased adverse outcomes among primary THA patients. In addition, we will explore whether controlled hypotension continues to be an effective technique for reducing intra-operative blood loss with modern surgical techniques and in the setting of widespread use of tranexamic acid.

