4.0 STUDY HYPOTHESES

This is retrospective study hypothesize that:

- A. There is no association between level and duration of hypotension with (i) myocardial infarction (MI), (ii) cerebrovascular accident (CVA), (iii) death in primary total hip arthroplasty patients.
- B. With the use of IV tranexamic acid is administered, the use of deliberate neuraxial anesthesia induced hypotension does not result in a further clinically relevant reduction in calculated blood loss after total hip arthroplasty.

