5.0 STUDY DESIGN

5.1 Endpoints

5.1.1 Primary Endpoint

The primary outcomes are the incidences of:

- i. myocardial infarction (MI)
- ii. cerebrovascular accident (CVA)
- iii. death
- iv. calculated perioperative intraoperative blood loss.

All primary outcomes are events during the inpatients stay.

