6.2 Inclusion Criteria

All primary THA patient data with sufficiently complete intraoperative vital signs will be included in the study.

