7.1 Data Collection

The following data will be collected:

Pre-operative/Baseline

- MRN
- Age
- Height
- Weight
- BMI
- ASA classification
- Ethnicity
- Gender
- Baseline status: METS, substance hx, smoking hx, SOB
- Comorbidity: OSA, COPD, asthma, HTN, CAD, CHF, Arrhythmia, pulmonary hypertension, seizure, TIA/CVA, renal dx, DM (type I or type II), coagulopathy, hx of dvt/PE
- Pre-op medications: beta-block, asa, anti-coagulant, nsaid, steroids
- Blood pressure: pre-op BP, and all intra-op

Intra-Operative

- Blood pressure: pre-op BP and all intra-op
- Intra-op medications: TXA IV or topical, ketamine, blood transfusion, albumin, IV fluids, epinephrine, ephedrine, phenylephrine, hydralazine, labetalol

Post-Operative

- Laboratory results: hemoglobin, BUN, creatinine

- Post-operative medications: (first 24 hours) IV fluids, albumin, blood transfusion, epinephrine, ephedrine, phenylephrine
- Complications: MI, CVA, death, ARF, pneumonia, arrhythmia, DVT, PE

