8.0 STATISTICAL ANALYSIS

1. Proposed analysis (e.g., student's t-test, ANOVA, chi-square, regression, etc.):
Two-step logistic regression modeling to determine odds ratios
2. Confidence intervals: 95%
3. Total sample size required: 10,000

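### Section 8 makes no allowance for clustering by anesthesiologist; if both hypotension and the outcome vary by provider after adjustment, ordinary 95% intervals for blood loss and commoner binary outcomes are too narrow

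*Combined protocol and SAP*

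**What the plan says.** Section 8.0 has three lines: "Two-step logistic regression modeling to determine odds ratios", 95% confidence intervals, and a sample size of 10,000. The synopsis repeats the first two. Neither names a provider term, a random effect, GEE or a clustered standard error. The two steps are not defined.

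Three other places bear on this.

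- Section 2.0 says that at this hospital "many anesthesiologists routinely manage the blood pressure in the 40-60 mmHg MAP range". The exposure is therefore at least partly a matter of who gives the anesthetic.
- Section 5.1.1 makes "calculated perioperative intraoperative blood loss" a primary outcome. Hypothesis B in Section 4.0 is that, with IV tranexamic acid, deliberate hypotension "does not result in a further clinically relevant reduction in calculated blood loss". Section 8.0 names no model for this continuous outcome.
- The synopsis lists "anesthesia provider name" and surgeon among the variables. Section 7.1, which opens "The following data will be collected", lists neither.

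**The concern.** Patients of one anesthesiologist share that person's blood-pressure habits. They may also share other things that affect blood loss or transfusion. When the exposure and the outcome residual are both correlated within provider, the patients carry less independent information on the association than a count of 10,000 suggests, and an ordinary standard error is too small.

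Both conditions are needed. Section 2.0 makes the first plausible without quantifying it. The documents say nothing on the second.

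What is at stake is mainly the interval for blood loss. Hypothesis B claims that no clinically relevant further reduction exists, yet the documents give no margin and no decision rule. Readers will judge relevance from the interval itself, so its width should be right.

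**Working it through.** **Inputs.** From the documents: N = 10,000 and 95% intervals (Section 8.0), at a single site (Section 5.2), so the clusters are providers rather than centers. Assumed, because the documents give none of them: number of anesthesiologists K (40 to 80, central 60), equal caseloads, exposure ICC ρx (0.05 to 0.2, central 0.2), outcome ICC ρy after adjustment (0.01 to 0.05, central 0.02), SD of blood loss (300 to 700 mL, central 500), an even exposure split, and half the patients receiving IV tranexamic acid. The plan has no figure of its own to reproduce here: 10,000 comes with no effect size, event rate, SD or power.

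**Formulas.** m = N/K; variance inflation VIF = 1 + (m − 1)·ρx·ρy; correct width = √VIF times ordinary width; two-sided error of the ordinary interval = 2·[1 − Φ(1.96/√VIF)]; coverage = 1 − error.

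Central case: m = 10,000/60 = 166.7; VIF = 1 + 165.7 × 0.2 × 0.02 = 1.663; √VIF = 1.289; effective N = 10,000/1.663 ≈ 6,014; error = 2·[1 − Φ(1.520)] = 12.8%.

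| N | K | ρx | ρy | VIF | Width factor | Coverage | Error |
|---|---|---|---|---|---|---|---|
| 10,000 | 60 | 0.20 | 0.02 | 1.663 | 1.289 | 87.2% | 12.8% |
| 10,000 | 60 | 0.05 | 0.02 | 1.166 | 1.080 | 93.0% | 7.0% |
| 10,000 | 80 | 0.05 | 0.01 | 1.062 | 1.031 | 94.3% | 5.7% |
| 10,000 | 40 | 0.20 | 0.05 | 3.490 | 1.868 | 70.6% | 29.4% |
| 5,000 | 60 | 0.20 | 0.02 | 1.329 | 1.153 | 91.1% | 8.9% |
| 5,000 | 80 | 0.05 | 0.01 | 1.031 | 1.015 | 94.7% | 5.3% |
| 5,000 | 40 | 0.20 | 0.05 | 2.240 | 1.497 | 81.0% | 19.0% |

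If ρx = 0 or ρy = 0, VIF = 1 and nothing changes.

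**In millilitres.** Half-width = 1.96·SD·√(4/N)·√VIF. At SD 500 and N = 10,000: 1.96 × 500 × 0.02 = 19.6 mL, and 19.6 × 1.289 = 25.3 mL. At SD 300 it goes from 11.8 to 15.2 mL, and at SD 700 from 27.4 to 35.4 mL. At SD 500 and N = 5,000 it goes from 27.7 to 32.0 mL.

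**Simulation, continuous outcome.** In the central case the ordinary interval had error of 0.11 to 0.13 and the clustered interval 0.048 to 0.056. With exposure ICC 0, ordinary error was 0.049 to 0.053; with outcome ICC 0 it was 0.048. At the low end of the range it was 0.048, so no problem could be detected there. Unequal (log-normal) caseloads raised ordinary error to 0.141 at log-SD 0.5 and 0.198 at log-SD 1.0, against 0.048 and 0.068 clustered.

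**Simulation, binary outcomes** (60 providers, exposure ICC 0.2, provider SD 0.3 on the log-odds scale, two runs each):

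| Outcome rate | Ordinary error | Clustered error |
|---|---|---|
| 15% | 0.081, 0.096 | 0.045, 0.053 |
| 5% | 0.055, 0.079 | 0.039, 0.060 |
| 0.3% (30 events in 10,000) | 0.050, 0.033 | 0.049, 0.034 |

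**What clustering does not do.** With an assumed correlation of 0.3 between a provider's habit and that provider's effect on the outcome, the clustered interval still had error of 0.28 to 0.30, because the estimate itself is biased. Anesthesiologist fixed effects brought it to 0.043 (0.053 with no correlation). Their width relative to the ordinary interval is about √[(1 − ρy)/(1 − ρx)] = √(0.98/0.80) = 1.11, or 19.6 × 1.11 ≈ 21.7 mL in the central case.

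**The case against.** The strongest reply is that the size rests wholly on assumptions. That stands. The same wording in Section 2.0 would fit near-uniform practice among the anesthesiologists, which would make the exposure ICC low. The range runs from negligible to serious, and the central effect is about 5 mL of half-width.

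A second reply is that blood loss has no stated model, so there is no planned interval to criticise, and that the undefined two steps might include provider. The first part stands to this extent: naming the model comes before choosing its standard error. The second is possible, but nothing in the text says so, and two-step does not mean two-level.

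A reader might infer more than the documents support:

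- *That all primary outcomes are affected.* MI, CVA and death are three of the four, and at about 0.3% their intervals are essentially nominal.
- *That variation in outcome between providers is enough.* It is not; the exposure must cluster too.
- *That Hypothesis B has an inflated false-positive rate.* No margin or decision rule is given, so no such rate can be stated. The error figures describe interval coverage only.
- *That 10,000 is too few.* The documents give no basis for that number, so it cannot be tested.
- *That surgeon fixed effects are needed as well.* They change the adjustment set, which is a different question from interval width. In logistic models with 30 surgeons they failed to converge in every replicate at about 30 events. A threshold of 10 events per surgeon would not rescue them: at 300 events, some surgeon has no event in about 10% of draws under moderately unequal caseloads and nearly 80% under very unequal ones.

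**Conclusion.** The omission is a fact of the text, and Section 2.0 supports half of the mechanism. The consequence is conditional: ordinary intervals for blood loss and commoner binary outcomes are too narrow only if exposure and outcome both vary by anesthesiologist after adjustment. On the central assumptions the shortfall in coverage is about 8 points (95% to 87%); if only half the patients had IV tranexamic acid and Hypothesis B is tested in them, it is about 4 points (95% to 91%). It matters most if relevance is judged in tens of millilitres, or if provider variation lies near the upper end of the range.

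This is a minor point and a cheap improvement. It does not invalidate the plan, and it concerns the width of intervals, not confounding by provider.

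**What to change.** Add to Section 8.0:

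> Calculated blood loss will be analysed by linear regression. All models, linear and logistic, will use standard errors clustered on anesthesiologist, whatever the number of events. As a sensitivity analysis, the blood-loss model will be refitted with anesthesiologist fixed effects, because clustering corrects interval width only and does not remove confounding by provider.

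Add anesthesia provider and surgeon to the Section 7.1 list, so that it matches the synopsis. That mismatch is worth repairing whatever the ICCs turn out to be.

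No event-count cut-off is needed, since clustered standard errors behaved as well as ordinary ones at 30 events. The inclusion rule in Section 6.2 ("All primary THA patient data with sufficiently complete intraoperative vital signs will be included in the study") is untouched, because no patients are removed.

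The cost is three sentences and two list entries, using fields already planned and a standard software option. The price is wider intervals where clustering is present, and almost none where it is absent: with outcome ICC 0, simulated error was 0.046 clustered against 0.048 ordinary.

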7.0 PROCEDURES

The independent variables of interest include extent of intraoperative hypotension (MAP <45, 50, 55, 60 mmHg) and duration of hypotension (5 mins interval). Intraoperative blood loss will be calculated based on pre-operative and post-operative laboratory hemoglobin levels.

The outcome variables include MI, CVA, death, intraoperative blood loss, ARF, pneumonia, arrhythmia, DVT, PE, and number of packed red blood cell (pRBC) transfusions.

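### Surgeon has no stated role in the blood-loss and transfusion analysis and is missing from the Section 7.1 data list, so between-surgeon differences could be attributed to hypotension.

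*Combined protocol and SAP*

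**What the plan says.** The synopsis data list includes "surgeon• duration of surgery• duration of anesthesia", next to the name of the anesthesia provider and any helpers. The detailed list in Section 7.1 has no surgeon and no provider. For the operation itself it covers blood pressure ("Blood pressure: pre-op BP, and all intra-op") and intraoperative drugs, fluids and transfusion.

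Section 8.0 has three lines: "Two-step logistic regression modeling to determine odds ratios", 95% confidence intervals, and a sample size of 10,000. It does not define the two steps, names no adjustment variable, and gives no model for a continuous outcome.

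Calculated blood loss is a primary outcome (Section 5.1.1) and transfusion a secondary one (Section 5.1.2). Hypothesis B in Section 4.0 is that, when IV tranexamic acid is used, hypotension "does not result in a further clinically relevant reduction in calculated blood loss after total hip arthroplasty". No margin is attached to it. Section 2.0 asks whether "controlled hypotension continues to be an effective technique for reducing intra-operative blood loss with modern surgical techniques". Section 6.3 excludes anterior and revision operations.

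**The concern.** The exposure in Section 7.0 (depth and duration of low MAP) arises from practice. Who operates can affect blood loss directly. It may also be related to pressure, either because surgeons prefer different pressures or because they work regularly with particular anesthesiologists. If both links exist, a comparison across all patients mixes the effect of pressure with differences between surgeons.

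The direction matters for Hypothesis B. If surgeons with higher blood loss tend to have lower pressures, a real saving is hidden. If surgeons with lower blood loss do, a saving appears that is not there. A sample of 10,000 does not reduce this bias; it puts a narrow interval around it. The patient variables in Section 7.1 (age, BMI, ASA class, comorbidity) do not measure surgical technique. As written, nothing commits the study to using surgeon, and the two data lists disagree on whether it will be extracted.

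**Working it through.** **The plan's own figure.** The 10,000 cannot be reproduced, because no power, effect size, SD, event rate or exposure split is given. For context, an assumed 5,000 against 5,000 at two-sided 5% with 80% power detects (1.960 + 0.842) × √(2/5,000) = 0.056 SD. Small differences would therefore reach significance.

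**Bias in blood loss.** Every input here is assumed: exposure scaled to SD 1, with share s = 0.20 of its variance between surgeons; surgeon SD of mean loss σ = 75 to 150 mL; surgeon-level correlation ρ between hypotension and loss of 0.3 to 0.5; residual SD 400 mL; true effect -50 mL per SD of exposure.

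Pooled slope = true effect + ρ × σ × √s, with √0.20 = 0.447.

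| ρ | σ (mL) | bias (mL) | pooled, ρ positive | pooled, ρ negative |
|---|---|---|---|---|
| 0.3 | 75 | 10.1 | -39.9 | -60.1 |
| 0.5 | 75 | 16.8 | -33.2 | -66.8 |
| 0.3 | 150 | 20.1 | -29.9 | -70.1 |
| 0.5 | 150 | 33.5 | -16.5 | -83.5 |

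The bias is 0.025 to 0.085 of the assumed 400 mL SD (10/400 to 34/400). The within-surgeon standard error is 400/√(10,000 × 0.80) = 4.5 mL, so the bias is 10.1/4.5 = 2.2 to 33.5/4.5 = 7.4 standard errors. Simulation with 40 surgeons and 1,000 data sets per setting agreed: pooled means of -40 to -17 mL and -60 to -83 mL, and within-surgeon means of -50 mL throughout. The within-surgeon empirical SD was about 4.5 mL, against 7 to 12 mL pooled. If only 5 to 10% of exposure variance lies between surgeons, the bias at ρ = 0.3 runs from 0.3 × 75 × √0.05 = 5 mL to 0.3 × 150 × √0.10 = 14 mL.

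**A second check with no true effect.** Take two equal groups of surgeons, with share a of one group's patients hypotensive and 1 - a of the other's.

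- Blood loss, groups 100 mL apart: spurious difference 100 × (2a - 1) = 20, 40 and 60 mL at a = 0.6, 0.7 and 0.8.
- Transfusion, 5% in the first group and 8% in the second: at a = 0.6 the rates are 0.6 × 5% + 0.4 × 8% = 6.2% with hypotension and 6.8% without, an odds ratio of 0.91. At a = 0.7 and 0.8 it is 0.82 and 0.74.
- At a = 0.5 the bias is zero for both.

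A simulation with 20 or 40 surgeons, surgeon SD 60 mL and 400 runs per setting gave a mean spurious difference of 23 to 25 mL at correlation 0.5, with false-positive rates of 0.67 to 0.80. With surgeon fixed effects the mean was within 1 mL of zero and the rate 0.03 to 0.06. At zero correlation there was no material mean bias. The unadjusted false-positive rate was still 0.15 (40 surgeons) to 0.27 (20 surgeons), because pressure use still clustered by surgeon in that simulation.

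**The case against.** A reader might infer that the plan excludes surgeon, or commits to pooling all patients. It does neither. Section 8.0 names no covariate at all, and the undefined second step could include surgeon. Age, ASA class, tranexamic acid and anesthesia provider are equally unmentioned. The documented fault is an adjustment set left open.

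A reader might also infer that surgeons at this hospital do work at different pressures, so that the estimate will be biased. Section 2.0 attributes pressure management to anesthesiologists. It gives a better surgical result as one of their aims, but does not say that surgeons ask for or receive different pressures. Its remark on modern technique, read with Section 3.0, is about change over time rather than variation between surgeons. Excluding anterior and revision operations removes two sources of difference, and the synopsis lists type and duration of surgery, which may capture some of the rest.

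The size is also wholly assumed, and both signs are possible. Hypothesis B concerns a clinically relevant reduction with no margin stated, so nobody can say that a shift of 10 to 34 mL would decide it. The within-surgeon estimate recovers the truth in simulation because no other confounding was built in.

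All of this stands, and it makes the point conditional. It does not remove the case for pre-specification: the documents do not rule the association out, and pairing of surgeons with anesthesiologists would be enough to produce it.

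**Conclusion.** The point holds as a conditional one. Surgeon appears in the synopsis only and has no stated role in the analysis of a primary outcome under a non-randomized exposure. If pressure practice and usual blood loss are related across surgeons, surgeon differences in blood loss and transfusion could be attributed to hypotension. Under the assumed inputs the bias is about 10 to 34 mL per SD of exposure, in either direction; it is zero if surgeon and pressure are unrelated. The documents establish neither the association nor its size or sign, and do not support saying that the bias will occur or that it would settle Hypothesis B. It should be corrected before analysis, because a within-surgeon estimate removes this source of bias whether or not it proves to be present.

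**What to change.** - Reconcile the two data lists by adding surgeon to Section 7.1.
- In Section 8.0, name a linear model for continuous calculated blood loss, which the stated logistic method does not fit. Include surgeon fixed effects, so that the hypotension effect is estimated within surgeon.
- Condition or stratify the transfusion model on surgeon.
- Preferably, report the between-surgeon component separately, so that readers can see whether it differs.

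**Cost.** No new patients or procedures are needed, and the synopsis already lists the field. It is more than one added term, because a blood-loss model must first be written. Surgeons who never vary pressure add little to the within-surgeon estimate, and surgeons with no transfusions add little to the transfusion model. The surgeon term does not deal with confounding inside a surgeon's own cases, such as bleeding that itself lowers pressure, and the plan should say so.

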3.0 OBJECTIVE(S) OF CLINICAL STUDY

The goal of this study is to determine if hypotensive neuraxial anesthesia is associated with worse outcomes in Primary Total Hip Arthroplasty (THA). There is a substantial body of literature supporting the safety and utility of the practice of deliberate neuraxial hypotension for reduction of blood loss during THA. However, substantial controversy remains regarding the safety of deliberate and controlled intraoperative hypotension with epinephrine mediated cardiac output augmentation as compared to inadvertent and/or uncontrolled intraoperative hypotension. Moreover, it is unclear if advances in surgical practice combined with the widespread use of TXA have diminished the clinical utility of deliberate hypotension as a means of minimizing blood loss. Therefore, this study is looking at the extent and duration of hypotension under neuraxial anesthesia in primary THA surgery.

This proposed project will be the largest study on deliberative hypotensive neuraxial anesthesia and adverse outcome in total hip arthroplasty. It will provide essential feedback and guidance to our clinical practice, indicating whether we need to modify our intra-operative management for better patient outcomes and less adverse complications, or conversely may allow us to argue that deliberate hypotensive neuraxial anesthesia is not associated with adverse events.

We will be accessing and reviewing EPIC data of patients who have undergone Primary Total Hip Arthroplasty at HSS from January 2016- December 3, 2018

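### Outcomes are stated as incidences and a null result may be used to argue safety, but only odds ratios are planned, which alone do not show how many extra events the data still allow

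*Combined protocol and SAP*

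**What the plan says.** Section 5.1.1 introduces myocardial infarction (MI), cerebrovascular accident (CVA), death and calculated blood loss with the words "The primary outcomes are the incidences of", and adds "All primary outcomes are events during the inpatients stay". Section 5.1.2 lists the secondary outcomes as incidences too.

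The whole of Section 8.0 is three items: "Two-step logistic regression modeling to determine odds ratios", 95% confidence intervals, and "Total sample size required: 10,000". The synopsis repeats the first two. Neither place mentions a risk by exposure level, a standardised risk, a risk difference or a method for sparse events.

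Hypothesis A in Section 4.0 is "There is no association between level and duration of hypotension" and each of MI, CVA and death. Section 3.0 gives the study a practical purpose, "indicating whether we need to modify our intra-operative management for better patient outcomes", or else supporting the argument that the technique is not linked to harm. The exposure in Section 7.0 is "extent of intraoperative hypotension (MAP <45, 50, 55, 60 mmHg) and duration of hypotension (5 mins interval"), with no share of patients given for any level.

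**The concern.** A finding of no association is meant to carry weight in a decision about practice. The reader of such a finding needs to know how much excess harm the data have not ruled out. An odds ratio answers that only when a baseline risk is put beside it, and the plan does not promise one.

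For example, take an upper confidence limit of 3 for the odds ratio. At an assumed baseline risk of 0.05% the odds are 0.0005003. Three times that is 0.0015008, a risk of 0.00150, or about 1.0 extra event per 1,000. At an assumed baseline of 1% the odds are 0.010101. Three times that is 0.030303, a risk of 0.0294, or about 19.4 extra per 1,000. The same reported limit could therefore describe very different amounts of possible harm.

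The risk to the study is that its safety conclusion is stated only as a relative measure, and cannot be set beside a blood-loss result expressed in volume.

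**Working it through.** **The plan's own figure.** The 10,000 cannot be reproduced. No event rate, target effect, power or exposure split is given.

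**Inputs.** From the documents: N = 10,000 and 95% intervals (Section 8.0). Assumed, because not stated: risk 0.1%, 0.5% or 1% per outcome; 50% or 10% of patients exposed; equal true risk in both groups; no covariate adjustment.

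**Formulas.**
- Odds ratio (OR), Wald: exp(±1.96 × SE), with SE = √(sum of 1/cell over the four cells).
- Risk difference (RD), Wald half-width: 1.96 × √[p(1−p)(1/n₁ + 1/n₀)].
- RD, Newcombe: Wilson limits for each group, combined by square-and-add.

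**0.1% risk, even split (5/5,000 vs 5/5,000).**
- OR: SE = √(2/5 + 2/4,995) = 0.633, giving 0.29 to 3.46. The exact conditional limits are 0.23 to 4.35.
- RD, Wald: 1.96 × √(0.001 × 0.999 × 2/5,000) = 0.00124, or ±1.24 per 1,000.
- RD, Newcombe: the Wilson limits in each group are 0.43 and 2.34 per 1,000. √(1.34² + 0.57²) = 1.46, or ±1.46 per 1,000.

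**0.1% risk, 10% exposed (1/1,000 vs 9/9,000).**
- OR: SE = √(1 + 1/999 + 1/9 + 1/8,991) = 1.055, giving 0.13 to 7.90.
- RD, Newcombe: the Wilson limits are 0.18 and 5.64 per 1,000 (exposed), 0.53 and 1.90 (unexposed). Upper limit √(4.64² + 0.47²) = 4.67; lower limit −√(0.82² + 0.90²) = −1.22. The interval is −1.2 to +4.7 per 1,000.

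**Higher risks, even split.**

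| Risk | Events per group | OR 95% CI | RD half-width per 1,000 (Wald) | Half-width ÷ baseline |
|---|---|---|---|---|
| 0.1% | 5 | 0.29–3.46 | 1.24 | 124% |
| 0.5% | 25 | 0.57–1.74 | 2.76 | 55% |
| 1% | 50 | 0.67–1.48 | 3.90 | 39% |

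**No events in one group.** For 0/5,000 the exact upper limit of that group's risk is 1 − 0.025^(1/5,000) = 0.74 per 1,000. This is a limit for one group, not for a difference. The OR still has a limit: for 0 vs 5 events in equal groups the estimate is 0, and the exact upper limit solves approximately (1/(1+ψ))⁵ = 0.025, so ψ = 0.025^(−1/5) − 1 = 1.09. The OR estimate is undefined only when neither group has an event.

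**Stability of a standardised risk difference.** With one exposed event among 10,000 patients, a simple bootstrap resample omits that event with probability (1 − 1/10,000)^10,000 ≈ 0.37. In such resamples an unpenalised logistic model has no finite exposure coefficient. A standardised difference from a model with roughly 5 to 20 events inherits that instability.

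**The case against.** A reader might infer that odds ratios are uninformative for MI, CVA and death. The documents do not support this. They give no event rates, so the rarity is itself assumed. At 0.5% to 1% the interval is reasonably precise. Where events really are rare the odds ratio approximates the risk ratio, so the scale is incomplete rather than misleading.

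A reader might also infer that a risk difference would bound the harm tightly. It uses the same few events and adds no information. At a 0.1% risk with an even split, +1.24 per 1,000 still allows the risk to more than double. With 10% exposed the upper limit is 4.7 per 1,000. No margin for harm is stated, so there is nothing against which to call either figure tight. The zero-event case does not rescue the inference, because exact limits exist for the odds ratio as well.

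It can further be said that Hypothesis A is one of no association, which an odds ratio addresses, and that the word incidences is used loosely, since calculated blood loss stands in the same list. The plan also sets no explicit trade of events against blood saved. All this is fair. It shows that the odds ratio is a legitimate measure to keep. It does not supply the absolute figure needed once a null result is used to argue safety or guide practice.

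**Conclusion.** The point holds as a gap in reporting and interpretation. No absolute measure is planned anywhere, although the outcomes are stated as incidences and the result is meant to inform practice. The gain from adding one is that the remaining uncertainty can be read as extra events per 1,000. It is not a gain in precision.

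How wide that uncertainty will be cannot be settled from the documents. Under the assumed 0.1% risk, the upper limit for excess harm runs from about 1.2 to 1.5 per 1,000 with an even split to 4.7 per 1,000 with 10% exposed. These figures are unadjusted and assume equal true risk; adjustment would change them. Section 7.0 has four pressure cut-offs by duration, so small exposed groups are plausible, but their size is unknown.

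**What to change.** Amend Section 8.0 and the matching synopsis row as follows.

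- For each binary outcome, report the number of events and the risk at each exposure level, and a standardised risk difference per 1,000 with 95% interval, beside the odds ratio.
- When events are few, use a penalised (Firth) logistic model with few covariates, or a propensity score, in place of an unpenalised multivariable model.
- In sparse or zero-event groups, use score or exact intervals for both the odds ratio and the risk difference.
- Interpret Hypothesis A by the upper limit of the risk difference. The plan states no margin, so the limit should be presented as the excess still compatible with the data. How much excess would matter is for the investigators to judge, preferably on record before the results are seen.

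The cost is some wording and a modest amount of code; the design and data stay the same and the odds ratio is kept. The downside is that absolute differences depend on this hospital's baseline risk and transfer less readily elsewhere, which is a reason to report both scales.
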